• To compare the effects of PIT versus TAU on key psychological measures: suicidal ideation, depression, hopelessness, self-esteem and wellbeing, on the level of harm resulting from self-harm incidents, on the frequency of self-harm thoughts, and on the participant's ACCT status at 8 weeks.

Outcome measures

Primary outcome

	IRAS No: 241606	
WORSHIP III		

The primary outcome is the total number of self-harm incidents in the 8-week period from baseline. We shall also be measuring the total number of self-harm incidents in the 12-weeks from baseline. All self-harm which takes place at a specific time point will count as one incident. For example, if someone cuts themselves on their neck and arm at the same time this will count as one incident; however, if they cut themselves at two different times, in the same day, this will count as two incidents e.g. when there is a gap of 30 minutes between incidents. This approach is consistent with the way incidents of self-harm are recorded on SystmOne and the prison self-harm records e.g. the self-harm incidents log/ACCT/NOMIS/F213.

The primary outcome will be a composite of self-harm incidents derived from self-report, medical databases (SystmOne) and prison databases or paper records (NOMIS; F213 forms, ACCT folders, self-harm incidents logs; daily officer's logs) checked for double entry. This approach was recommended in Borschmann et al (2017) who conclude that relying on one data source for self-harm incidents in incarcerated adults could substantially under-ascertain the actual number of events [23]. Self-harm acts will be recorded on the self-harm incidents logs (participants, prison and SystmOne) and then checked for double entry before they are entered into the CTU database. The date and time of each self-reported incident will be recorded to allow cross-checking with medical and prison records, which record self-harm incidents by date and time, to check for duplication.

Both the intervention group and the control group will be asked to complete a weekly self-harm incidents' log (participants) outlining the number of times they have self-harmed since the last entry. All participants (in control and intervention arm) will be able to self-complete the log, at the end of one week, or complete the log with a research assistant. We will explore with each prison recruiting trusted peers to assist with log completion if the women have low literacy.

Secondary outcomes

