Consent for participation in the research will be sought by the research assistants or associate/CSOs/research nurses associated with the project. All people who seek participants' consent will act in accordance with the study protocol, the principles of good clinical practice (GCP) and the Declaration of Helsinki. All people who are authorised to take consent will be recorded in the Delegation Log. Although initial screening will be carried out without prior consent, we will seek consent from the women prisoners to examine their prison and healthcare notes for all the additional data to be collected during to the research e.g. primary outcome data and resource use data. During the consent process we will collect contact details for the women in case they are released early from the prison, and shall seek to contact them via their probation office or their Community Rehabilitation Company (CRC). If the participant is released part way through the therapy, we will let their probation officer know about their involvement. We shall also seek the women's consent for a transfer hold to be enacted so they remain in the study prison during the intervention period. We shall seek consent to contact the women in another prison if they are transferred despite this. To ensure that the prison and healthcare staff are aware of their participation we shall seek consent to send a letter to the participant's prison GP and mental health team and record participation in the research in the participant's ACCT records and on NOMIS and SystmOne. We will also seek permission to tell the woman's personal officer that they are taking part in the research project and Safer Custody, healthcare and OMU staff. We shall also seek consent to add information about risk to their ACCT records, NOMIS and SystmOne and to discuss risk with relevant staff. This will include alerting healthcare to any undiagnosed mental illness which is revealed during the research interviews or therapy. These measures are necessary safeguarding and women who do not agree will be unable to take part in the research.

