All participants will provide written informed consent before participation in any of the research procedures. A photocopy of this consent form will be added to the participant's medical notes along with a page outlining the study title, acronym, version number and date of the relevant PIS and the date that consent was obtained. These documents will also be given to the Forensic Team for secure filing.

The PIS will outline the participants' right to refuse participation without giving reasons. It will also explain to participants that they are free to withdraw at any time from the trial without giving reasons and without prejudicing any further treatment. At baseline, participants will be asked to provide consent for any data that has been collected up to the point of withdrawal to be used after withdrawal. If participants do not consent to this retention, all data will be destroyed. This will apply to all participants in the trial, however, staff in the focus groups will be informed that it may not be possible to destroy their data if they withdraw from the focus group.

The PIS and consent forms for the women prisoners taking part in the trial will outline that participation in the research will not affect the women's parole, the standard of care they receive in the prison or any other aspect of their life in prison in any way. It will also outline circumstances when the researchers/therapists will have a duty to disclose information to prison staff. The research team will be required to disclose the following information to all the relevant departments in the prison:

	IRAS No: 241606
WORSHIP III	IKAS NO. 241000

- Behaviour that is against prison rules
- Information that either indicates a risk or harm to yourself or others
- Information on undisclosed illegal acts or plans to commit a new
- crime
- Information that raises concerns about terrorism, radicalisation, or security.
- information about poor or unacceptable practices by prison staff or by an outside organisation

The team are also required to report information about risk of harm to self to healthcare/ mental health in-reach. Any risks identified will also be reported to the Trial Manager. Women will be encouraged to disclose these risks to staff themselves, if they do not want to do this, we will ask for permission to inform staff; if both options are refused, researchers will inform the prison without consent.

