Where a participant is able to consent but later becomes incapacitated, the participant will be suspended from the study. If their capacity returns they will be given the opportunity to re-enter the study. When a participant is formally withdrawn from the study, by their own choice or due to ongoing incapacity, identifiable data already collected with consent will be retained and used in the study, if they consented to retention at baseline. No further data will be collected, or any other research procedures carried out, on or in relation to the participant.

Randomisation

WORSHIP III	IRAS No: 241606

Kings Clinical Trials Unit will build a randomisation system. Randomisation will be at the individual level by block randomisation with randomly varying block sizes, stratified by prison. The trial manager/RAs will access the randomisation system, randomise the participants and receive randomisation alerts and will inform the other researchers and the therapists of the allocation for each participant.

Blinding

Blinding of trial participants and care providers is not possible due to obvious differences between the interventions. It is not practical for the research assistants/research associate to be blind as they will need to coordinate the delivery of the therapy in their study prisons. The outcome assessors who collect the post intervention data (8-weeks) and follow-up data (12-weeks) will be blind to the intervention groups. Outcome assessors will include trained Research Nurses/CSOs/volunteers/peer mentors/ students. These outcome assessors will be security trained so they can enter the prison independently to complete their assessments and will have no other involvement in the research. The trial manager will ensure that outcome assessment takes place at a time and in a location of the prison which will avoid the assessors interacting with the RAs and therapists in a way that could reveal any participant's allocation. If a participant is transferred to a remote site which cannot be accessed by the outcome assessors, they will be followed up by a research assistant who is unaware of their randomisation status. E.g. the RA from London will follow up the RA from Manchester's participants.

Emergency Unblinding

Emergency unblinding should not be necessary as the investigators and therapists will not be blinded and will be able to respond to any serious adverse events in accordance with the protocol.

Baseline data

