- Long-term follow up assessments at 12-weeks will be collected during a 1-hour interview with a blind outcome assessor and will include all secondary outcome measures (BSS; BDI-II; BHS; RSE; WEMWBS) and the health related quality of life measures (EQ-5D-5L; SF-12).
- The participant's ACCT status will be recorded by the research assistant.
- We shall also collect from NOMIS the amount of time that each participant spent on a basic regime from 8 weeks to 12 weeks.

Prison-level data collection

We shall collect the following information on the Prison-Level data collection form:

- The average amount of time that women spend outside their cells for each of the study prisons in one week
- Whether the prison provides an in-cell telephone service.

Qualitative assessments

12-20 individual interviews (6-10 from the control group and 6-10 from the intervention group) will be completed with pilot women at 10-12-weeks to determine if there are any issues or problems with participation which need to be addressed before the full-scale trial. These interviews are designed to help to inform the decision regarding progression, for example, if a rescue plan is necessary.

During the full-scale trial, process evaluation interviews will be completed with 40 women prisoners (20 from the intervention group and 20 from the control group) at 10-12-weeks. These interviews will be designed to explore the opinions of the participants on PIT or TAU and any problems they encountered in relation to the implementation of the intervention in the prison. Staff process evaluation focus groups will be undertaken in all prisons (N=7; 8-12 per group) to explore their perceptions of TAU or PIT, for example, how they believe it affects the wellbeing of women in their care and any problems they encountered in relation to implementation of the treatment in their prison.

We will invite the therapists, research assistants and the outcome assessors to take part in individual qualitative process evaluation interviews.

Withdrawal and termination criteria

Women will be removed from the research if they wish to withdraw e.g. if they are finding participation too distressing. All women who withdraw will be asked to provide a reason. In WORSHIP II we found that approximately 65% of the women were happy to disclose why they no longer wished to participate

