An opportunity sample of 264 women will be recruited to the research. The sample size is powered to detect a minimal important clinical difference of 33% reduction in self-harm incidents over 8 weeks. This clinically significant difference is based on Hawton et al's systematic review of the efficacy of psychological and pharmacological interventions designed to reduce self-harm repetition [43]. From MOJ prison data, the average number of self-harm episodes over 8 weeks in the control group was 6.65 [3]. We modelled this with a Poisson distribution (mean and variance=6.65) and used Monte Carlo simulations with 1000 simulations to estimate the power for a range of sample sizes, with power defined as the proportion of estimated p-values less than 0.05 for null hypothesis testing (treatment effect is 0), against an alternative hypothesis (33% reduction in the log of the outcome). With 5% significance, to obtain 90% power, we will require 105 per group for the primary analyses. Based on WORSHIP II [6] we estimate 20% attrition so will recruit 132 per group at baseline. This level of attrition is not expected in the primary outcome, due to availability of prison data and the fact that self-reported incidents will be measured on a weekly basis, but allows for attrition in the secondary outcomes.

We expect that there will be several potential therapists because we are using trainees as well as qualified professionals. This means that each therapist will see a small number of participants each (mean≈6.6). In turn, we expect that the ICC will be small (though no estimates are available to inform our calculations), and since the number of participants per cluster is also small, the corresponding design effect indicates a small increase to the sample size would be required to take into account this clustering. We anticipate that this will be balanced by accounting for baseline prognostic factors in our statistical models, and that 90% power will be maintained with lower than 20% attrition rate for the primary outcome. We shall include a random effect for each therapist within the statistical analysis models.

Planned recruitment rate

The predicted figures have been calculated based on the number of women who will pass through each of the prisons, depending on their size and the recruitment rate achieved in WORSHIP II. The predicted figures (confirmed by HMPPS) are calculated as follows:

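### Formal withdrawal ends extraction from prison and healthcare records as well, although the sample size section counts on those records to keep primary-outcome attrition below 20%

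*Protocol*

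**What the plan says.** The last paragraph of the protocol's Consent section sets the rule. It applies "When a participant is formally withdrawn from the study, by their own choice or due to ongoing incapacity", and states: "No further data will be collected, or any other research procedures carried out, on or in relation to the participant". Data already collected are kept only if the woman agreed to this at baseline. Otherwise, the same section says: "If participants do not consent to this retention, all data will be destroyed".

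Withdrawal and termination criteria gives the trigger: "Women will be removed from the research if they wish to withdraw e.g. if they are finding participation too distressing".

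The primary outcome depends on the sources that the rule switches off: "The primary outcome will be a composite of self-harm incidents derived from self-report, medical databases (SystmOne) and prison databases or paper records". Access to them rests on baseline consent: "we will seek consent from the women prisoners to examine their prison and healthcare notes for all the additional data". Nothing in the protocol says that this access may outlast withdrawal.

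Sample size calculation inflates for loss to follow-up: "we estimate 20% attrition so will recruit 132 per group at baseline". It then says of the primary outcome: "This level of attrition is not expected in the primary outcome, due to availability of prison data", with weekly self-report as a second reason. The next paragraph relies on primary-outcome attrition below 20%, together with adjustment for baseline prognostic factors, to hold 90% power although therapist clustering was not built into the calculation.

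**The concern.** Routine records are what should make this primary outcome robust. A woman can miss every log and interview and her incidents still appear in SystmOne, NOMIS, ACCT folders and F213 forms. The sample size section leans on this. The withdrawal rule removes it for the women most likely to have no self-report either, because weekly self-report also stops at withdrawal.

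The counts lost in this way may not be missing at random. The protocol's own example of a reason to withdraw is distress, and it also mentions not feeling a benefit from therapy. Ongoing incapacity is a further route. Each could be related to self-harm. The main analysis assumes missing at random, and the Statistical analysis plan section expects little missing data. Sensitivity analyses can model absent counts under different assumptions. They cannot recover counts that were never extracted, or that were destroyed.

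**Working it through.** **Setting the passages side by side**

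1. Consent: after formal withdrawal nothing more is collected, with no exception for records.
2. Primary outcome: records and weekly self-report are the only sources of the count.
3. Sample size calculation: records and weekly self-report are the two reasons why attrition should stay below 20%.
4. It follows that, for a formally withdrawn woman, both reasons fail from the day of withdrawal. Where retention was refused at baseline, her earlier data go too.
5. No section offers a middle course in which logs and interviews stop but record extraction continues.

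**Reproducing the protocol's figure**

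Inputs from Sample size calculation: 105 evaluable per group and 20% attrition.

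105 / (1 − 0.20) = 131.25, rounded up to 132 per group, or 264 in total. This matches. The 105 is taken as stated, and this point does not depend on how it was derived.

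**Margin left for therapist clustering**

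The protocol gives about 6.6 women per therapist and no ICC. Let *a* be the primary-outcome loss. The protocol does not say how much loss comes from formal withdrawal, so *a* = 0 to 20% is an assumed range.

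- Evaluable per arm: n = 132(1 − a)
- Largest design effect that still leaves 105 effective: DE = n / 105
- Women per therapist after loss: m = 6.6(1 − a)
- Largest ICC, with clustering in both arms: (DE − 1) / (m − 1)

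| a | n | DE | m | Largest ICC |
|---|---|---|---|---|
| 0% | 132 | 1.257 | 6.60 | 0.257/5.60 = 0.046 |
| 10% | 118.8 | 1.131 | 5.94 | 0.131/4.94 = 0.027 |
| 20% | 105.6 | 1.006 | 5.28 | 0.0057/4.28 = 0.001 |

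If only the PIT arm is clustered, and the two arms have equal variance, these ICCs double to about 0.092, 0.053 and 0.003. The pattern is the same.

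**Power, taking 90% at 105 as given**

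Power = Φ(3.2415 × √(n / (105 × DE_c)) − 1.96), where 3.2415 = 1.960 + 1.2816 and DE_c = 1 + (m − 1) × ICC. With an assumed ICC of 0.02 in both arms:

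- a = 0%: DE_c = 1.112, power 93%
- a = 10%: DE_c = 1.099, power 91%
- a = 20%: DE_c = 1.086, power 88%

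Without clustering, power is 95% at no loss and 90% at 20% loss.

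**Direction of any bias**

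Suppose there is no true effect, withdrawn women have *r* times the rate of the others, and they are dropped altogether. The observed rate ratio is then (1 + w_TAU(r − 1)) / (1 + w_PIT(r − 1)), where w is the share withdrawn in each arm. With assumed values r = 2, w_PIT = 15% and w_TAU = 5%, it is 1.05/1.15 = 0.913, an apparent 9% reduction. With the two shares exchanged it is 1.15/1.05 = 1.095, an apparent 10% increase. The protocol supplies none of these inputs, so the sign is not known.

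**The case against.** The strongest reply is that the rule is narrower than it looks, and much of this stands.

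- **Stopping therapy is not withdrawal.** A reader might infer that any woman who gives up therapy loses her primary outcome that day. The documents do not support this. Withdrawal and termination criteria treats stopping the intervention for an individual as a separate matter. Assessment and management of risk foresees therapy ending early on transfer, and Trial Procedures plans continued measures after transfer. The analysis keeps randomised women whatever their compliance and models the number of sessions received.
- **The sample size is not made wrong.** The 20% inflation is already in the 132. The protocol says only that loss at that level is not expected, not that there will be none. It also counts on covariate adjustment to offset clustering, and records still protect against transfer, missed logs and missed interviews.
- **Missing data are not ignored.** The protocol plans a missing-at-random main analysis on all available data, multiple imputation if required, and imputation of a range of values under missing not at random. A reader might also infer that a truncated count would be modelled as a full 8-week count, since no exposure term is mentioned. Such handling is commonly left to the SAP, which is not at hand, so the inference is not supported.
- **Differential withdrawal is unproven.** The Background reports that, in the pilot, women were unlikely to drop out because of the arm they were in.
- **Scope of consent is partly a design choice.** The consent form is not at hand. The amendment history says that some of its items are mandatory and others are not, and data are destroyed only where a woman refused retention.

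What remains is that the protocol, as written, ends record extraction at formal withdrawal while citing those records as its protection against loss. An optional item on the consent form would not change the wording of that rule.

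**Conclusion.** The point holds in a limited form. The withdrawal rule and the attrition argument do not fit together for formally withdrawn women, and no stated option keeps their record-based counts. The consequence is avoidable missing data in the primary outcome, possibly for outcome-related reasons, and erosion of the margin that the protocol sets against therapist clustering.

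The size depends on a formal-withdrawal rate that is not given. Over the assumed range of 0 to 20% loss, 132 down to about 105 women per arm remain, and the tolerable ICC falls from about 0.046 to about 0.001 with clustering in both arms. The power figures rest on an assumed ICC and on the protocol's claim of 90% at 105, before any gain from covariate adjustment. No bias of stated size or direction can be claimed. This is an inexpensive improvement that should be made; it does not invalidate the design.

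**What to change.** Amend Consent, Withdrawal and termination criteria, the information sheet and the consent form to separate three decisions:

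- (a) stopping therapy;
- (b) stopping logs and interviews;
- (c) withdrawing permission to use records.

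Ask at baseline for permission to go on extracting self-harm incidents from prison and healthcare records to week 12 unless the woman chooses (c). Keep handling after loss of capacity subject to the ethics committee's approval. Record the level and date of each withdrawal, and the last date of record coverage for each woman, so that incomplete counts can be identified in the analysis.

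The permission has to be sought prospectively, because access cannot simply be resumed after withdrawal under the present wording. No new data source is needed, and a woman can still end all use of her records. The cost is a protocol and consent amendment with its approvals, and some women may decline the item.

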- Participants will be asked to complete a weekly Self-Harm Incidents' Log (Participants) which will record acts of self-harm and the severity of these acts. The log will be self-completed by the participant, with a peer mentor or completed with a research assistant. This will be cross referenced with prison and healthcare records using the Self-Harm Incidents' Logs (prison and SystmOne).
- Participants will be asked to complete a weekly Concomitant therapies form. The forms will be completed with a research assistant. This will be cross referenced with prison and healthcare records, if necessary.
- The research assistant will complete the Concomitant Medications Log on a weekly basis using SystmOne.
- Post intervention assessments at 8-weeks will be collected during a 1-hour interview with a blinded outcome assessor and will include all secondary outcome measures (BSS; BDI-II; BHS; RSE; WEMWBS) and the health related quality of life measures (EQ-5D-5L; SF-12).
- The participant's ACCT status will be recorded by the research assistant.
- Participants randomised to receive PIT will be asked to complete the Therapy Satisfaction Questionnaire at 10 weeks with an unblinded member of the research team.
- We shall also collect from NOMIS the amount of time that each participant spent on a basic regime from baseline to 8 weeks.

Long term follow-up assessments

• Participants will be asked to complete a weekly diary which assesses self-harm thoughts and life events which may affect people's self-harm, including the amount of time that the participant has spent outside their cell. The diary will be self-completed by the participant, with a peer mentor or completed with a research assistant.

	IRAS No: 241606
WORSHIP III	

- Participants will be asked to complete a weekly self-harm incidents' log (participants) which will record acts of self-harm and the severity of these acts. The log will be self-completed by the participant, with a peer mentor or completed with a research assistant. This will be cross referenced with prison and healthcare records.
- Participants will be asked to complete a weekly Concomitant Therapies Form. The forms will be completed with a research assistant. This will be cross referenced with prison and healthcare records, if necessary.
- The research assistant will complete the Concomitant Medications Log on a weekly basis using SystmOne.

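### The protocol contradicts itself on who knows allocation and on assessor independence, so masking of the 8- and 12-week scale interviews is not secured for remote follow-up by a research assistant or for assessments by peer mentors

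*Protocol*

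**What the plan says.** **Who is told the allocation (Protocol, Randomisation).** The trial manager or RAs randomise, are alerted to the result and "will inform the other researchers and the therapists of the allocation for each participant". No site, region or role is excepted.

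**Who is masked (Protocol, Blinding).** Participants and therapists cannot be masked. On the RAs: "It is not practical for the research assistants/research associate to be blind as they will need to coordinate the delivery of the therapy"; the reason is tied to their own study prisons. For the interviews: "The outcome assessors who collect the post intervention data (8-weeks) and follow-up data (12-weeks) will be blind to the intervention groups". The pool from which these people are drawn is broad: "Outcome assessors will include trained Research Nurses/CSOs/volunteers/peer mentors/ students". The section adds that these people have no further part in the research, and that the trial manager will choose times and places that keep them apart from RAs and therapists.

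**Remote transfers (Protocol, Blinding).** If a woman moves to a site that the assessors cannot enter, "they will be followed up by a research assistant who is unaware of their randomisation status". The example given is that "the RA from London will follow up the RA from Manchester's participants".

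**What peer mentors also do (Protocol, Trial assessments and Long term follow-up assessments).** For the weekly Self-Harm Incidents' Log: "The log will be self-completed by the participant, with a peer mentor or completed with a research assistant". The same rule applies to the weekly diary, in both periods.

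**What is collected under the mask.** The 8- and 12-week interviews cover BSS, BDI-II, BHS, RSE, WEMWBS, EQ-5D-5L and SF-12.

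**The concern.** Participants and therapists know the arm, so masking of the interviewer is the main protection the protocol states for these scales. It guards against one specific bias: an interviewer who knows the arm and, without intending to, steers or records answers accordingly. All five psychological secondary scales depend on it. So does EQ-5D-5L, which drives the primary cost-effectiveness analysis (Economic evaluation).

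A team that follows the Randomisation sentence to the letter would tell the very RA who is later supposed to be unaware. A team that uses peer mentors in both of the roles given to them would have assessors who do have other involvement in the research. In either case the trial report could describe an assessment as masked when the written procedures did not secure that. Who receives allocation alerts and who may assess outcomes are protocol matters, so this cannot be left to an analysis plan.

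**Working it through.** There is no figure to reproduce and no formula applies. The check is to set the passages side by side.

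**Route (a): the RA from another region**

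| Question | Randomisation | Blinding |
|---|---|---|
| Who learns the allocation? | The other researchers and the therapists, for each participant | RAs are unmasked in order to coordinate therapy in their own prisons |
| Does the London RA know a Manchester woman's arm? | Yes, if the sentence is applied as written | No; the remote route depends on it |

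1. An RA in another region is one of the other researchers on the ordinary meaning of the words.
2. The disclosure covers every participant, so it includes women who later transfer.
3. No sentence in Randomisation withholds allocation from RAs elsewhere. Emergency Unblinding also describes the investigators as unmasked without limit by site.
4. The two statements therefore conflict unless the first is narrowed to staff at the same site, which the protocol does not do.

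**Route (b): peer mentors**

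| Question | Blinding | Trial assessments / Long term follow-up |
|---|---|---|
| What do peer mentors do? | Assess outcomes at 8 and 12 weeks, masked | Help with the weekly diary and the weekly log |
| Other involvement in the research? | None | Up to weekly contact over research forms |

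1. As a role, peer mentors cannot both have no other involvement and help with weekly forms.
2. The protocol does not say that one individual does both. Apart from the general condition that assessors have no other involvement, which the role as described already contradicts, nothing bars it.
3. Helping with a log does not in itself disclose the arm. The diary does cover life events and time out of cell, so a helper could come to learn that a woman attends weekly therapy. That is a possibility, not something the text establishes.
4. The stated safeguard separates assessors from RAs and therapists. It does not deal with what an assessor learns from the participant.

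**Other listed assessors.** Research nurses and CSOs also take consent and do baseline interviews, so the no-other-involvement statement is loose for them too. Those tasks come before randomisation and cannot reveal the arm. No text clearly tells nurses, CSOs, volunteers or students the allocation.

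**Extent.** The protocol plans 3-5 prisons as follow-up sites only, but does not say which, if any, the assessors cannot enter. It gives no expected number of such transfers and no share of interviews to be done by peer mentors. The number of affected interviews cannot be calculated.

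**The case against.** The best reply is that the documents show what was meant. The specific rule that the remote RA is unaware should govern the general sentence about telling other researchers. Reading that sentence as covering everyone would unmask the outcome assessors as well and empty the Blinding section. The reason for unmasking RAs is confined to their own prisons. The amendment history agrees with the current Blinding text: it records a clarification that RAs will not know the arm of another RA's participants. On peer mentors, the no-other-involvement condition could be read as already barring anyone who helps with logs. Peer help is something the team will explore with each prison, assessors are to be security trained so as to enter independently, and the form recording therapies is completed with an RA, not a peer.

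Most of this stands as evidence of intent. It does not put the intent into the procedure that staff will follow. The Randomisation sentence is the instruction on disclosure and still has no limit. The peer-mentor role is undefined and appears under the same name in both tasks.

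It is also fair that assessor masking cannot remove bias from women who know their own arm, and that transfer holds and the requirement for 8 weeks remaining in prison should limit transfers. Both points reduce the stakes. Neither resolves the contradiction.

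A reader might go further and infer that masked follow-up fails wherever it is claimed, or that some definite share of the 264 women will have unmasked data. The documents support neither. The other assessor roles can remain masked, a separation safeguard is stated, and no figure exists from which to derive a share.

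**Conclusion.** The concern holds in limited form. Masking of the 8- and 12-week interviews is not secured for two routes: an RA from another region following up a woman transferred to a site the assessors cannot reach, and a peer mentor acting as assessor. Route (a) is the firmer of the two: applied as written, one sentence defeats the other. Route (b) is a conflict of roles. It becomes a loss of masking only if the same person does both tasks and learns the arm.

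The extent is unknown. The affected outcomes are the five psychological scales and the two quality-of-life measures. The primary outcome is outside this point: it is built from weekly logs, which may be completed with unmasked RAs, together with prison and healthcare records, and the masked interviews do not supply it. The conclusion assumes that the other researchers means what it says, and that peer mentor denotes the same kind of person in both places. If the sponsor can show that neither is so in practice, what remains is wording to tidy. This is worth correcting, but it does not threaten the primary analysis.

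**What to change.** 1. **Randomisation.** State that allocation goes only to the trial manager, the RA(s) at the participant's own prison and her therapist, and that RAs in other regions have no access to it. Set the alert and login permissions in the randomisation system to match.
2. **Blinding.** State that anyone who has helped participants with diaries or logs in a prison may not assess outcomes in that prison. Say whether the peer mentors named as assessors are the same group as those who help with weekly forms.
3. **Optional.** Add one item to the 8- and 12-week forms recording whether the assessor knew the allocation, so that the extent can be reported.

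The cost is protocol wording and a permission setting. No extra staff should be needed, since nurses, CSOs, volunteers and students are already listed as assessors. The downside is a slightly smaller assessor pool in prisons where peers help with the weekly forms.
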